4.0 OVERVIEW OF STUDY DESIGN/INTERVENTION

4.1 Design

This study is a non-therapeutic open observational trial, which evaluates the feasibility of the hyperspectral camera system (a non-significant risk device) in evaluation of the tissue perfusion and oxygenation in different circumstances. The exploratory aim of this study is to select relevant spectral bands for oxygenation and perfusion detection, which can be used for further camera development and consequently in clinical practice. Eight healthy volunteers, without any medication use and without any relevant medical history will be included in this study. Subjects will be enrolled following confirmation of study eligibility (section 5.0) which will be checked at baseline. Reproducibility will be validated by performing the following HCS measures:

- Basal blood flow
- Blood flow upon occlusion-reperfusion brachial artery
- Blood flow after applying capsaicin-based cream
- The room temperature, which could influence the skin perfusion will also be measured.

For the secondary endpoints, hyperspectral measures of:

- basal blood flow / oximetry
- blood flow /oximetry upon occlusion-reperfusion brachial artery
- Blood flow / oximetry after applying capsaicin-based cream

Reproducibility will be validated by the HCS measure only, at both time points that the HCS is used.

Explorative endpoint:

The explorative endpoint of the study is to see if a selection of spectral bands, specific for tissue perfusion and oxygenation (selected after data processing of above mentioned measurements) can be achieved.

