An emerging technique is hyperspectral imaging, which is capable to detect the scattering and absorption of light delivered to the tissue, caused by inhomogeneity of biological structures, such as haemoglobin, fat or water [11]. In vivo real-time imaging of the perfusion is currently not possible, however snapshot imaging was used to evaluate oxygen levels in the retina, which was quite complex, especially the part of data processing [12, 13]. Recently, a novel hyperspectral imaging camera (Quest Medical Imaging BV, Middenmeer, The Netherlands) has become available as prototype. This device allows non-invasive measurement of skin blood flow, oximetry and (vascular) anatomy, only based on the endogenous contrast of the tissue. Therefore it could be used to obtain non-invasively information about the (superficial) anatomical structures and moreover to measure the microvascular condition.

However the capability of this device to pick up physiological changes is unknown. To validate this hyperspectral camera system (HCS) for measuring skin blood flow and vascular anatomy the following study is proposed:

- Measurement of forearm skin blood flow before, during and after occlusion of the brachial artery;
- Measurement of local changes in skin blood flow after applying a local capsaicin-based cream (local vasodilator);

Read outs from the HCS after local application of capsaicin-based cream will be compared to measurements of an untreated area of the forearm. Furthermore, the changes in these measurements will be evaluated over time..

Hyperspectral camera system:

Hyperspectral imaging is a non-invasive optical technique, using halogen light as a light source, which is also widely used in commercially available light sources. Halogen light could produce some heat, however imaging will be performed on a distance of 50 centimetres. The technology used in this camera, is partially comparable to the technology used in Diffuse Reflectance Spectroscopy, which has been used in diverse clinical studies in the Netherlands Cancer Institute without reporting of any side effects during the measurements [17, 18].

Summary of findings from non-clinical studies

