4.2 Intervention

The capability of the HCS in detection of tissue perfusion and oxygenation in eight human volunteers during different circumstances: before/after occlusion brachial artery, before/after application capsaicin-based cream..

Quest Hyperspectral imaging system

The HCS is not approved by the US Food and Drug Administration. The device qualifies as non-significant risk because it is not used as an implant, nor is it used to sustain human life, nor will it be used in diagnosing, curing, mitigating or treating disease and does not present a potential for serious risk to the health, safety, or welfare of a subject.

The device is designed for medical applications and has optimized optics for spectral analysis of biological compounds. In this camera 3 sensors are combined for optimal spectral imaging. For 2D reference, and to facilitate annotating the data, a high resolution (full HD) color image, recorded with an RGB-sensor, is included with each hyperspectral dataset. The spectral bands are acquired using a 4x4 mosaic sensor for the spectral range of 470 – 630 nm, this sensor is referred to as the VIS-sensor. The NIR-sensor is a 5x5 mosaic sensor with a spectral range of 600 – 950 nm (see Figure 1 for an impression of the transmission bands of the sensor pixels). The color image is co-registered with the hyperspectral data with subpixel accuracy, making accurate data fusion and visualization methods possible.

This hyperspectral camera is based on a tiled-filter approach where pixels are individually filtered with narrow Fabry-Pérot bandpass filters. This method allows real-time imaging at video frame rates without the need to scan in either the spatial dimension (e.g. moving the camera) or the spectral dimension (e.g. changing the pass-through characteristics of an optical filter).

The Quest hyperspectral imaging system has 41 spectral bands, equally distributed in the visible-near infrared (VIS-NIR) range of the electromagnetic spectrum (450 – 950 nm). The time it takes to capture the hyperspectral images and obtaining feedback from the instrumentation is around 2-3 seconds, which is nearly real time. The field of view is 10 x 10 centimeter, which makes this camera system suitable for clinical use in the future. It delivers images with a 10 frames per second framerate.

[figure not shown]
The device has been supplied to MSK by Quest Innovations.

Data analysis HCS

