After each measurement of a specific tissue part, a 3-dimensional hypercube with a corresponding graph could be created after data processing as illustrated in this figure [11].

The HCS consists of three sensors, creating three images, that have to be merged to a 3D datacube. Before merging, the images has to be analysed. In general, hyperspectral image analysis will consist of preprocessing, feature extraction and selection, and classification. Noise could be removed by preprocessing part of data analysis by diverse denoising techniques. After denoising, the images could be merged to a 3D datacube. Afterwards, feature extraction will be applied to select clinically relevant spectral bands for perfusion and oxygenation measurements. Finally, principle component analysis is used to reduce redundant information in the bands of hyperspectral imagery while preserving as much of the variance in the high dimensional space as possible [11].

Non-Investigational products:

1. Capsaicin crème FNA 0,75 mg/g Capsaicin-based cream is a selective 'transient receptor potential vanilloid 1-receptor' (TRPV1) agonist. It is registered for use in the treatment of local itch, post herpes neuralgia or diabetic polyneuropathy. The compound has been selected because of it induces release of vasoactive neuropeptides causing vasodilatation.

The medication will be administrated cutaneously, according to the prescription. We will use the commonly used concentration of cream for clinical practice.

The cream will be administrated cutaneously. Capsaicin cream we will use a 0.075% dosage.

The cream will only be used during this feasibility study to induce vascular changes in healthy human volunteers. The cream will be supplied by the MSK pharmacy as per standard single patient ordering procedures. We aim to detect these small vascular changes with the hyperspectral camera. If the camera is able to detect these changes, it has the potential to detect small vascular changes in patients with bad vascular perfusion for whatever reason (vascular diseases, surgical intervention etc.). We will emphasize that the medication is not necessary for using the hyperspectral camera, however it is only used to induce vascular changes.

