11.0 BIOSTATISTICS

Primary study parameter(s)

Reproducibility is measured by performing the measurements on two different days in the same study population. Sample T-tests will be used for comparison of the perfusion

measured by the HCS system and room temperature in the eight recruited human volunteers. The intra-subject variability over the two measurement moments will be established by calculation of the coefficient of variation.

Secondary study parameter(s)

For spectral measurements no specific statistical analysis is performed. It is mainly a part of data processing as described in the study design protocol section 4.0.

Leiden University Medical Center (LUMC) is utilizing their own protocol under their own regulatory body oversight, and conducting separate but similar protocols. LUMC data will be pooled with our data for analysis.

The PI of this study will be sharing de-identified data with an external collaborator at Leiden University Medical Center for the purpose of data analyses. Anonymized images taken from the hyperspectral camera will be electronically sent to Quest Medical Imaging for analysis.

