13.0 DATA MANAGEMENT ISSUES

Radiology research staff will be assigned to manage this study. Radiology clinical research coordinator and a regulatory research associate will be responsible for protocol compliance, data collection, data abstraction and entry, data reporting, regulatory monitoring, adverse event tracking and reporting, SAE reporting, regulatory submissions, problem resolution and prioritization, and coordinate the activities of the protocol study team.

Source documentation will be available to support the computerized patient record. All research material from this study will be handled with the same confidentiality as patients' medical data records.

MSK data will be collected in a secure, restricted departmental database. The PI of this study will be sharing de-identified data with an external collaborator at Leiden University Medical Center for the purpose of data analyses. Anonymized images taken from the hyperspectral camera will be electronically sent to Quest Medical Imaging for analysis.

Leiden University Medical Center (LUMC):

As a similar study is being done at LUMC, after the study is complete at MSK, we plan to share de-identified MSK data with LUMC for data analyses and to combine results. No participant identifiers to be shared.

Section 13.1 Regulatory Documentation

Prior to implementing this protocol at MSK, the protocol, informed consent form, HIPAA authorization and any other information pertaining to participants must be approved by the MSK Institutional Review Board/Privacy Board (IRB/PB). There will be two separate protocol documents and each site will utilize their own locally approved document.

Participating sites that are conducting data analysis should submit this protocol to their IRB according to local guidelines. Copies of any site IRB correspondence should be forwarded to MSK.

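### Spectral bands are selected from 41 candidates in eight volunteers plus pooled LUMC data, and the visible plan does not test them in anyone left out of the selection (minor; cheap to improve)

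*Combined protocol and SAP*

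**What the plan says.** All references are to the combined protocol and SAP.

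- **Endpoint.** Section 4.1 sets out to see whether "a selection of spectral bands, specific for tissue perfusion and oxygenation (selected after data processing of above mentioned measurements) can be achieved". It says the bands are for further camera development and, after that, clinical practice. Section 2.0 lists the same aim as a secondary objective; Section 4.1 calls it exploratory.
- **Candidates.** Section 4.2: "The Quest hyperspectral imaging system has 41 spectral bands".
- **Contrasts.** Section 3.0 plans "Measurement of forearm skin blood flow before, during and after occlusion of the brachial artery". Section 7.0 adds the capsaicin-treated region against control regions on the same forearm.
- **Method.** In Section 4.2, "feature extraction will be applied to select clinically relevant spectral bands for perfusion and oxygenation measurements". Afterwards, "principle component analysis is used to reduce redundant information in the bands of hyperspectral imagery". No ranking measure or number of bands to keep is given, and PCA is not described as the selector.
- **Statistics.** Section 11.0: "For spectral measurements no specific statistical analysis is performed". It refers the reader back to Section 4.0.
- **Other people.** Section 11.0: "LUMC data will be pooled with our data for analysis". Section 13.0: "we plan to share de-identified MSK data with LUMC for data analyses and to combine results". The number of LUMC volunteers is not stated.

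Section 18.0 lists a user manual and the LUMC protocol as Appendices 1 and 3. Their text is not available for this review.

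**The concern.** The same volunteers supply the data that choose the bands and the only data on which the bands can be judged. The second study day does not change this, because it measures the same people again: it can show whether a band is stable within a person, but not whether it works in a new one. LUMC volunteers are the only other people mentioned, and pooling adds them to the selection set when they could have served as a check on it.

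Some band will always come out on top. Without a check in people left out of the selection, a band that responds to perfusion or oxygenation cannot be told from one that happened to move consistently in this group. Later camera development would then rest on a choice whose reliability in new people is unknown. If a contrast for the selected bands is reported from the same people, it will also tend to be too large. The plan does not say that such a contrast will be reported, so this second consequence is conditional.

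**Working it through.** **Inputs from the plan.** Eight volunteers (Sections 1.0 and 4.1). Bands (Section 4.2): a 4x4 and a 5x5 mosaic sensor give 16 + 25 = 41, which reproduces the stated figure.

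**Assumptions, not in the plan.** Each volunteer contributes one within-subject change per band, with between-subject SD 1. Bands are ranked by |mean change / SD| and the top one is kept. This ranking rule is for illustration only. Five correlation patterns between bands are used: independent; AR(1) 0.90; AR(1) 0.99; exchangeable 0.95; exchangeable 0.99. Section 4.2 itself expects redundant bands, so the highly correlated patterns are the more plausible.

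**Left-out check.** Repeat the selection in seven volunteers, then read the chosen band, in the direction found in the seven, in the eighth. Average over the eight repeats.

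**1. No true response.** The best band shows an apparent mean change of 0.73 SD (independent) down to 0.35 SD (exchangeable 0.99). Left-out volunteers show about zero. For scale, a single band fixed in advance, with only its direction read from the data, has expected absolute mean √(2/(π × 8)) = 0.28 SD. Choosing among 41 bands therefore adds between 0.35 − 0.28 = 0.07 and 0.73 − 0.28 = 0.45 SD. The left-out check removes both parts.

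**2. True response present.** Two cases: the same 1 SD change in every band, and a response concentrated in a few bands with a 2 SD peak.

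| Pattern | 1 SD in all bands: apparent | Left-out | 2 SD peak: apparent | True value of chosen band | Excess (apparent/true − 1) |
|---|---|---|---|---|---|
| Independent | 1.445 | 0.999 | 2.043 | 1.786 | 14% |
| AR(1) 0.90 | 1.298 | 0.999 | 1.903 | 1.784 | 7% |
| AR(1) 0.99 | 1.130 | 0.996 | 1.963 | 1.933 | 2% |
| Exchangeable 0.95 | 1.102 | 0.994 | 1.970 | 1.930 | 2% |
| Exchangeable 0.99 | 1.052 | 0.996 | 1.983 | 1.963 | 1% |

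In the three highly correlated patterns the overstatement is 5 to 13% in the first case (1.052 to 1.130 against a true 1) and 1 to 2% in the second.

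**3. Pooling.** The LUMC number is not given, so totals are assumed. In the 1 SD case the apparent change across the five patterns is 1.395 to 1.046 with 12 volunteers in all and 1.273 to 1.023 with 32. Pooling shrinks the excess but does not remove it, and it leaves nobody outside the selection.

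**The case against.** The strongest reply is that this is an openly exploratory aim in a small feasibility study. The primary objective does not depend on band selection, and Section 11.0 plainly offers no inference on the spectra. That stands, and it sets the severity. The change of label between Sections 2.0 and 4.1 is clerical and does not raise it.

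The simulation has limits that also stand. The ranking rule is not the protocol's. The case with 1 SD in every band cannot show a wrong band being chosen, because every band is equally good; it shows only optimism in a contrast. With highly correlated bands and a real response, that optimism is small. What does not depend on these choices is that no visible section looks at the bands in anyone outside the selection.

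A method may also sit in Appendix 1 or 3, so absence is shown for the visible text only. Section 11.0, however, refers to Section 4.0 and not to an appendix.

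Three stronger readings are tempting, and the documents do not support them:

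- *The endpoint cannot fail, so it is empty.* There is indeed no stated cut-off, and what would make a band specific is not defined. But Section 3.0 says the device's ability to pick up physiological change is unknown, and Section 4.2 makes its potential conditional on the camera detecting the induced changes. A negative outcome is contemplated. What is missing is detail, and a fixed pass rule is not essential to an exploratory aim.
- *There is a high false-positive rate, such as 1 − 0.95^41 = 0.88.* The plan has no per-band test and no significance level, and real bands are correlated.
- *The bands are presented as validated for clinical use.* Section 1.0 says only that they could be used in clinical practice, and Section 4.1 puts further camera development first.

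**Conclusion.** The concern holds as a minor point. The visible plan chooses bands and would judge them on the same people, so it cannot show which bands carry over. With no true response, a best band would still appear, with an apparent change of 0.35 to 0.73 SD where left-out volunteers show about zero. With a true response and highly correlated bands, the overstatement is about 1 to 13%. These figures assume one band kept, eight volunteers, the ranking rule above and the stated correlation patterns, and none of these except the eight volunteers comes from the plan. The conclusion that a check is missing rests on the text and not on the figures, subject to what the unavailable appendices contain.

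**What to change.** Add to Sections 4.2 and 11.0 wording such as:

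> Band selection is repeated eight times, each time leaving out all images and both visits of one volunteer. For each contrast (occlusion versus baseline, reperfusion versus baseline, capsaicin region versus same-forearm control) we report the contrast in the left-out volunteer, using the bands and direction found in the other seven, and how often each band is selected. The number of bands kept, and how they are combined into one contrast, are fixed before the images are analysed. Where procedures are comparable, MSK-selected bands are checked in LUMC data before any pooled re-selection. Selected bands are reported as hypothesis-generating.

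If an appendix already holds a selection rule, cite it and add the left-out check.

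Selection frequency should not stand alone. With no response, some band is chosen in at least 7 of 8 repeats in 15 to 22% of simulated studies when one band is kept, and in 48 to 82% when three are kept.

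No pass rule, such as the expected direction in all eight left-out volunteers, is required. If the team wants an achieved/not-achieved cut-off, the choice is theirs, and its error rates should be computed for the number of bands actually kept. For example, at a true 1 SD in every band the 8-of-8 rule passes in 26 to 35% of simulated studies with one band kept, but in 25 to 76% with three bands kept.

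**Cost.** Wording and extra analysis code, agreed with LUMC and the camera company, which receive the data and images. No new volunteers, visits or images are needed, and checking LUMC data before pooling loses none of them. The downside is that the reported contrasts will look less favourable.

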4.2 Intervention

The capability of the HCS in detection of tissue perfusion and oxygenation in eight human volunteers during different circumstances: before/after occlusion brachial artery, before/after application capsaicin-based cream..

Quest Hyperspectral imaging system

The HCS is not approved by the US Food and Drug Administration. The device qualifies as non-significant risk because it is not used as an implant, nor is it used to sustain human life, nor will it be used in diagnosing, curing, mitigating or treating disease and does not present a potential for serious risk to the health, safety, or welfare of a subject.

The device is designed for medical applications and has optimized optics for spectral analysis of biological compounds. In this camera 3 sensors are combined for optimal spectral imaging. For 2D reference, and to facilitate annotating the data, a high resolution (full HD) color image, recorded with an RGB-sensor, is included with each hyperspectral dataset. The spectral bands are acquired using a 4x4 mosaic sensor for the spectral range of 470 – 630 nm, this sensor is referred to as the VIS-sensor. The NIR-sensor is a 5x5 mosaic sensor with a spectral range of 600 – 950 nm (see Figure 1 for an impression of the transmission bands of the sensor pixels). The color image is co-registered with the hyperspectral data with subpixel accuracy, making accurate data fusion and visualization methods possible.

This hyperspectral camera is based on a tiled-filter approach where pixels are individually filtered with narrow Fabry-Pérot bandpass filters. This method allows real-time imaging at video frame rates without the need to scan in either the spatial dimension (e.g. moving the camera) or the spectral dimension (e.g. changing the pass-through characteristics of an optical filter).

The Quest hyperspectral imaging system has 41 spectral bands, equally distributed in the visible-near infrared (VIS-NIR) range of the electromagnetic spectrum (450 – 950 nm). The time it takes to capture the hyperspectral images and obtaining feedback from the instrumentation is around 2-3 seconds, which is nearly real time. The field of view is 10 x 10 centimeter, which makes this camera system suitable for clinical use in the future. It delivers images with a 10 frames per second framerate.

[figure not shown]
The device has been supplied to MSK by Quest Innovations.

Data analysis HCS

After each measurement of a specific tissue part, a 3-dimensional hypercube with a corresponding graph could be created after data processing as illustrated in this figure [11].

The HCS consists of three sensors, creating three images, that have to be merged to a 3D datacube. Before merging, the images has to be analysed. In general, hyperspectral image analysis will consist of preprocessing, feature extraction and selection, and classification. Noise could be removed by preprocessing part of data analysis by diverse denoising techniques. After denoising, the images could be merged to a 3D datacube. Afterwards, feature extraction will be applied to select clinically relevant spectral bands for perfusion and oxygenation measurements. Finally, principle component analysis is used to reduce redundant information in the bands of hyperspectral imagery while preserving as much of the variance in the high dimensional space as possible [11].

Non-Investigational products:

1. Capsaicin crème FNA 0,75 mg/g Capsaicin-based cream is a selective 'transient receptor potential vanilloid 1-receptor' (TRPV1) agonist. It is registered for use in the treatment of local itch, post herpes neuralgia or diabetic polyneuropathy. The compound has been selected because of it induces release of vasoactive neuropeptides causing vasodilatation.

The medication will be administrated cutaneously, according to the prescription. We will use the commonly used concentration of cream for clinical practice.

The cream will be administrated cutaneously. Capsaicin cream we will use a 0.075% dosage.

The cream will only be used during this feasibility study to induce vascular changes in healthy human volunteers. The cream will be supplied by the MSK pharmacy as per standard single patient ordering procedures. We aim to detect these small vascular changes with the hyperspectral camera. If the camera is able to detect these changes, it has the potential to detect small vascular changes in patients with bad vascular perfusion for whatever reason (vascular diseases, surgical intervention etc.). We will emphasize that the medication is not necessary for using the hyperspectral camera, however it is only used to induce vascular changes.

